## **Monitoring**

### **Data monitoring**

A data monitoring committee will not be required for this trial as the interventions pose minimal risk, and participants will be protected by personal insurance throughout the study.

## **Harms**

All participants will have their adverse events monitored throughout the study, whether directly related to the intervention or not (if applicable). This monitoring will be done through self-reporting at the start of each session, registered for analysis and report purposes, or by their primary care physicians. Participants will be advised to contact the clinical team if they have difficulties.

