### **Interventions**

**Combined home-based exercise group.** Participants in this group will exercise throughout their chemotherapy treatments, starting within 1-2 weeks of its start and ending within 3-4 weeks post-treatment completion .

The exercise intervention will be led by qualified exercise professionals, comprising two weekly 60-minute online exercise group sessions with a 5-minute warm-

up, a 30-minute resistance training, and a 20-minute aerobic exercise component, finishing with a 5-minute cooldown . The warm-up will be composed of mobility and activation movements, such as cat-camels, butterfly chest stretch, overhead reach, floor angels, spine twist in sitting and alternated all fours position, doorway chest stretch, wall slides, scissors, pointer, and single leg stances. The resistance training component will consist of 9 different exercises, performed either with body weight or free weights, completing 2-3 sets of 10-15 repetitions, and will involve movements such as chair sit-to-stand, multi-directional lunges, calf, and toe raises, double-arm and one-arm rows, push-ups, glute bridges, clams, chest press, multi-directional shoulder raises, leg curls, and abdominal exercises (i.e., crunches, leg raises, crisscross) . The aerobic component will consist of low-impact dance exercises, moving large muscle groups to increase heart rate, involving marching, side steps, knee raises, leg curls, multi-directional arm movements, and dance movements . The cooldown will consist of breathing exercises and light stretches. Every exercise professional will follow a written protocol to ensure consistency in the intervention program's application .

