Before the beginning of the exercise program, participants will receive an education session on how to use Borg's Perceived Rate of Exertion Scale (RPE) to monitor their effort during aerobic and resistance training and tips on when they may increase the exercise intensity . During the training sessions, participants in the intervention group will be asked to choose their preferred load to execute each exercise in the resistance component, told to perform the aerobic exercises at their preferred speed, and informed that they can stop exercising whenever they need to rest. The exercise professional may suggest increasing loads in specific exercises, but these increases will not be imposed on the participants. Attendance to the sessions in the intervention and control groups will be registered. Additionally, women in this group will be encouraged to perform brisk walking at their preferred intensity and receive a pedometer to increase walking motivation .

**Control group.** Women randomized to the control group will receive weekly 30-minute supervised sessions with breathing, stretching, relaxation exercises, and meditation during the intervention period . Women in this group will not be forbidden to perform PA but will not receive any incentives or advice from the supervising exercise professional.

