### **Plans to promote retention**

The conducting exercise professional will control participants' adherence to the exercise program through a presence registry collected by the research team member with access to the list of participants' numbers. After the session, the non-interventionist research team member will pass the presence list to the respective numbers of the participants for program adherence analysis. If a participant fails to attend a session, contact will be made to ensure the participant's welfare and motivate them to participate

in the next session. The data analysis will not consider participants who fail to attend 50% or more sessions. Positive feedback will be given to the participants during the sessions, as positive feedback is proven to enhance feelings of competence, enjoyment, and interest in the activity . Additionally, participants will be encouraged to keep an activity diary where they may register all activities performed autonomously. Participants will be contacted one week before the assessment to confirm their availability and presence. Data from participants who fail to perform the assessments during the intervention period will be excluded from data analysis. After the intervention, participants will be contacted monthly to check their well-being and keep their interest and motivation in engaging in the follow-up assessment.

\*\*\* Table 2\*\*\*

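### Scheduled adverse-event questioning is twice weekly in the exercise arm, once weekly in control and tied to attendance, so reported harms may differ between arms without a true difference

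*Protocol*

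**What the plan says.** All adverse-event collection is described in the protocol's Harms section. It covers all participants throughout the study and includes events unrelated to the intervention. The scheduled route is: "This monitoring will be done through self-reporting at the start of each session, registered for analysis and report purposes". The same sentence adds a second route, "or by their primary care physicians", and the section closes with a third: "Participants will be advised to contact the clinical team if they have difficulties". Neither of these has a timetable, a form or a standard question.

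The Interventions section sets the session frequency. The exercise arm receives "two weekly 60-minute online exercise group sessions" and the control arm receives "weekly 30-minute supervised sessions with breathing, stretching, relaxation exercises, and meditation".

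Plans to promote retention deals with absence: "If a participant fails to attend a session, contact will be made to ensure the participant's welfare and motivate them to participate" in the next one. It does not say that adverse events are asked about or recorded at that contact. The same section plans monthly well-being contacts after the intervention, again without describing them as adverse-event collection. No section sets a common adverse-event schedule that is independent of attendance.

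**The concern.** How often people are asked affects how many events they report, especially brief or mild ones. These women are on chemotherapy, which the protocol's own background describes as having many side effects, so such events will be common in both arms. If one arm is asked every few days and the other once a week, a harms table by arm mixes true event rates with frequency of asking.

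Attendance adds a second difficulty. A woman too unwell to join a session is not put the session question that day. Under Criteria for discontinuing or modifying allocated interventions, a woman whose condition worsens may stop the sessions altogether, and with them the only scheduled query.

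Two errors are at stake. A spurious excess could make the exercise programme look less safe than it is, and missed reports among absentees could hide a real problem. The Data monitoring section dispenses with a committee on the ground of minimal risk, so the quality of this information matters. Later analysis cannot recover events that were never asked about.

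**Working it through.** The protocol gives no adverse-event rate and no harms comparison, so there is no stated figure to reproduce.

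**Inputs from the protocol.** Sessions per week: 2 (exercise) and 1 (control), from Interventions. Intervention length: about 6 months, from the Abstract, taken here as 24 weeks. Allocation 1:1. Total 98 women, from Sample size, hence 49 per arm (the Abstract's 122 would give 61).

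**Assumptions not in the protocol.** The two weekly sessions are evenly spaced, so the asking interval L is 3.5 days in the exercise arm and 7 days in control. The recall, duration and reporting parameters below are also assumed. True event rates are equal throughout, and ratios are exercise to control.

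**1. Number of scheduled questions.** Full attendance: 2 × 24 = 48 against 1 × 24 = 24, ratio 2.0. Over 26 weeks it is 52 against 26, the same ratio. With attendance a_E and a_C the ratio is 2 × a_E / a_C:

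| Attendance, exercise / control | Questions | Ratio |
|---|---|---|
| 100% / 100% | 48 / 24 | 2.0 |
| 75% / 75% | 36 / 18 | 2.0 |
| 75% / 50% | 36 / 12 | 3.0 |
| 50% / 75% | 24 / 18 | 1.33 |
| 50% / 100% | 24 / 24 | 1.0 |

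The ratio falls below 1 only if exercise attendance is less than half of control attendance.

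**2. Recall that fades (full attendance).** If the chance of reporting an event decays exponentially with time constant τ, the fraction captured is (τ/L) × [1 − exp(−L/τ)].

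| τ (days) | L = 3.5 | L = 7 | Ratio |
|---|---|---|---|
| 1 | 0.277 | 0.143 | 1.94 |
| 3.5 | 0.632 | 0.432 | 1.46 |
| 7 | 0.787 | 0.632 | 1.25 |
| 14 | 0.885 | 0.787 | 1.12 |
| no decay | 1.000 | 1.000 | 1.00 |

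**3. Only events present on the day are reported (full attendance).** For an event lasting D days the fraction captured is min(1, D/L). The ratio is 2.0 for D up to 3.5 days, 1.00/0.714 = 1.4 for 5 days, and 1.0 for 7 days or more.

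**4. Effect on a harms table, at the unfavourable end.** Suppose each question yields a report with constant probability q, whatever the interval since the last. The proportion with at least one report is 1 − (1 − q)^48 against 1 − (1 − q)^24.

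| q | Exercise | Control | Chance of a nominally significant difference, 49 per arm | 61 per arm |
|---|---|---|---|---|
| 0.01 | 38% | 21% | 44% | 53% |
| 0.02 | 62% | 38% | 65% | 75% |

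The chance is for a two-sided 5% comparison of proportions. With equal ascertainment it would be about 5%.

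**5. After the fix.** One weekly query in each arm gives 24 against 24 questions at the same 7-day interval. The expected ratio is 1.0 under equal true rates, provided response to the query is similar in the two arms.

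**The case against.** The strongest reply is that the protocol does not rely on sessions alone. The Harms section also names physicians and invites women to contact the clinical team, and a missed session triggers an individual welfare contact. A reader might infer from the session-based wording that absentees are never asked about adverse events. The documents do not support that: these routes reach absentees. What can be said is that none of them carries a defined adverse-event question or schedule, so they do not equalise ascertainment.

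Second, a reader might infer that reported harms will be inflated in the exercise arm. That is not established either. A weekly question can pick up everything since the previous one, and the calculations give no distortion with complete recall or with events lasting a week or more. Serious events are likely to be least affected. Lower attendance in the more demanding arm could offset the imbalance. All of this stands, and it limits the claim to a liability to differ, mainly for short or minor events.

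Third, adverse events are not among the listed outcomes, and Statistical methods plans no between-arm harms test. Tabulation may be left to an analysis plan that is not available here. That is fair as to tabulation. But the protocol registers these events for analysis and reporting, and the collection schedule is fixed in the protocol itself.

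Fourth, the session question is not the only information bearing on safety. Chemotherapy dose and duration come from medical records in both arms, and the staff registering clinical information are to be blinded to group. Dose changes and interruptions are thus captured independently of sessions, although symptoms and injuries that do not alter treatment are not.

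**Conclusion.** The point holds in a limited form. Following the protocol as written, the only scheduled adverse-event question is asked at a 2:1 ratio in favour of the exercise arm at equal attendance, and it depends on attendance. The other routes are unstructured and do not correct this. Reported events may therefore differ between arms with no true difference.

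The 2:1 ratio of questions follows directly from the stated session frequencies. Its effect on reported events rests on assumed recall, event duration and even spacing of sessions: a ratio of about 1.0 to 2.0 at equal attendance. Differential attendance can push the imbalance in questioning above 2 or cancel it, and reverses it if exercise attendance is below half of control attendance. Neither the size nor the direction of the net bias can be fixed in advance. The primary outcome is not affected. The weakness concerns the harms report, and it is worth correcting before enrolment because it cannot be repaired afterwards.

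**What to change.** Put one identical weekly adverse-event query to every randomised woman in both arms, whether or not she attends. A short online form would do, since the study already sends its questionnaires by email as online forms. Use the planned missed-session contact as back-up, and state that it includes the same question.

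Base the by-arm harms summary on that weekly query. Record the source of every report, so that session-prompted, spontaneous and physician reports can be listed separately without entering the comparison on unequal terms.

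Restricting the question to the first session of each week would equalise frequency but would still miss absentees, so it is not sufficient.

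The cost is slightly more participant burden, plus the work of setting up and tracking one short form. Non-response to the form should be reported by arm, since equal asking removes the bias only if response is similar.

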## **Auditing**

Two authors will supervise all trial procedures and cross-check the interventionist actions and study processes. Additionally, an independent person external to the project will review the protocol.

## **Ethics and dissemination**

### **Research ethics approval**

This study has received ethical approval from the collaborating hospital (UAIF 069/2024). This trial will follow the World Medical Association's Declaration of Helsinki for Human Studies.

### **Protocol amendments**

Any changes to the protocol will be promptly communicated to all participants involved in the study or data manipulation. The lead investigator will inform all cooperating institutions, sponsors, or funding agencies. Modifications to the protocol will be submitted for approval to all the Ethics committees involved in the project. The published protocol or the informed consent form will be amended, and updated, if necessary.

### **Consent or assent**

Healthcare professionals will approach potential participants to determine if they are interested in participating. If they express interest, they will be referred to a research team member who will contact them. Additionally, interested participants will be allowed to share the study information with other women who have been diagnosed with breast cancer. If any of these women express interest in participating, they will also be considered after obtaining medical clearance. Once the eligibility criteria for the study are confirmed and the women express their interest in participating, they will receive the Informed Consent through email. In the informational session, women will be asked to digitally fill out and sign the Informed Consent. It will be clear to the participants that they can withdraw their consent anytime. After the informational session, a PDF copy of the signed Informed Consent will be emailed to each participant. The research team will also take additional measures to collect and share the participants' data.

### **Confidentiality**

The responsible members of the investigation will maintain all datasets on a secure server of CIDEFES-UL for ten years. These datasets will be used solely for research purposes. Datasets utilized for specific analyses or sub-studies will only contain the necessary variables and the demographic indicators provided to the research team members upon request by the leading investigator.

### **Declaration of interests**

The authors declare no competing interests.

### **Access to data**

The corresponding author will make anonymized trial data available for non-commercial research purposes upon reasonable request.

### **Ancillary and post-trial care**

Post-trial care is unnecessary as no harm is expected during the trial. However, an insurance policy will cover participants if needed during the study.

### **Dissemination policy**

This trial's findings will be disseminated through publication in leading international oncology scientific journals and presentations at national and international conferences. In addition, the results and mediation analysis will be produced and published. As this is a pragmatic trial with highly applicable outcomes for participants and decision-makers, it presents potential for future widespread implementation through relevant stakeholders.

### **Authors' contributions**

[name] conceived the project and wrote the manuscript. [name] revised and edited the manuscript and will randomly assign participants' numbers and random allocation. [name] and [name] assisted in project refinement and revised and edited the manuscript. Also, the former authors will supervise the entire trial.

### **Acknowledgements**

We thank [name] for facilitating open communication between the Hospitals and the research team. Without the action of this medical professional, the successful implementation of this study would be compromised.

### **Declaration of Generative AI and AI-assisted technologies in the writing process**

While preparing this work, the authors utilized Grammarly's AI-powered writing assistance to enhance the manuscript's language and readability. Subsequently, the authors reviewed and edited the resulting content as necessary, taking full responsibility for the publication's final version.

## **Discussion**

The Home-Combo study aims to expand the knowledge regarding the effects of a supervised home-based combined exercise program for women undergoing neo-adjuvant and adjuvant chemotherapy for breast cancer. The incidence of breast cancer has been increasing steadily over the years, particularly among women. In specific home-based exercise training programs, exercise training programs have already been proven safe for women with BC during the treatment phase. Studies conducting structured and supervised home-based exercise programs in women with BC during the treatment phase are still scarce. Furthermore, since this study also includes participants performing neo-adjuvant chemotherapy, it will be possible to verify the effects of the intervention in a prehabilitation (i.e., pre-operative) context. Also, according to [name] et al., there is a need for more studies that analyze the effects of exercise on chemotherapy completion rates. Lastly, to the authors' knowledge and according to the research, no studies have conducted an exercise intervention where the intensity of the performed exercise is self-selected by the participants in a sample with a diagnosis of BC during treatments. Therefore, this study may give a significant contribution to robust knowledge regarding home-based exercise programs in women with BC diagnosis undergoing chemotherapy treatment. Also, this study is expected to have immediate benefits to all women with BC enrolling in this study and a potential impact on improving interventions designed to promote higher adherence to the study and active lifestyle behaviors. The online alternative and the dissemination of an easy-access exercise program that can be performed at home might be particularly important for the region where the study will be conducted, since public transportation is not very effective, and many people live in remote areas with little to no access to a nearby sports or exercise facilities. If the hypothesis are confirmed, or if at least results show that women with a BC diagnosis can stick to the planned chemotherapy sessions and doses, with little to no interruptions and no dose adjustments, the results will potentially represent less time to treatment exposure, quicker return to everyday life, fewer side effects, and better overall and disease-related quality of life.

